3.1.3 BICR assessment using irRECIST 1.1

The criteria that built the foundation for irRC were the WHO criteria which existed before the publication of RECIST 1.1. The irRC are, therefore, like WHO criteria, based on bi-dimensional measurements (Wolchok et al 2009). More recently, RECIST 1.1 has become the gold standard for disease status determination for study subjects with solid tumours. To be more in line with RECIST 1.1 criteria, irRC has been adjusted so that uni-dimensional measurements are used (referred to as irRECIST 1.1). This modification of irRC 2009 criteria (irRECIST 1.1) is suggested based on the results of Nishino et al 2013, who found that irRC using the unidimensional measurements provide highly concordant response assessment compared with the bi-dimensional irRC, with less measurement variability. Furthermore, this enables a consistency with RECIST 1.1 which enables a clearer contrast of the results from the two methods than would otherwise be possible.

The definitions of CR, PR, SD and PD according to irRECIST 1.1 are outlined clearly in the Independent Review Charter (referred to as irCR, irPR, irSD/irNN and irPD in that document), but a brief description of the methodology is given here.

In irRECIST 1.1 the presence of new lesions will not automatically trigger a declaration of Progressive Disease, but instead new lesions can be measured and these measurements will be added to the sum of diameters of the target lesions. Based on the sum of these measurements and % calculations thereof, the target lesion + new measured lesion response assessment will be derived. The overall response assessment (irCR, irPR, irSD/irNN, irPD, irNE or irND) will be obtained at the BICR and confirmation of PD is required. The imaging scans will be reviewed by 2 independent radiologists and will be adjudicated, if required.

Where stated, the endpoints in Section 3.2 will also be derived using these assessment methods for supportive purposes.

3.1.4 Site investigator assessment using RECIST 1.1: target lesions

Measurable disease is defined as having at least one measurable lesion which is ≥ 10 mm in the longest diameter (except lymph nodes which must have short axis ≥ 15 mm) with CT or MRI and which is suitable for accurate repeated measurements.

A patient can have a maximum of 5 measurable lesions recorded at baseline with a maximum of 2 lesions per organ (representative of all lesions involved suitable for accurate repeated measurement) and these are referred to as TLs. If more than one baseline scan is recorded then measurements from the one that is closest to randomisation will be used to define the baseline sum of TLs. It may be the case that, on occasion, the largest lesion does not lend itself to reproducible measurement in which circumstance the next largest lesion, which can be measured reproducibly, should be selected.

All other lesions (or sites of disease) not recorded as TL should be identified as NTL at baseline. Measurements are not required for these lesions, but their status should be followed at subsequent visits.

Note: For patients who do not have measurable disease at entry (i.e. no TLs) but have non-measurable disease, evaluation of overall visit response at each visit will be based on the overall NTL assessment and the absence/presence of new lesions (see Section 3.1.6 for further details). If a patient does not have measurable disease at baseline then the TL visit response will be not applicable (NA).

For patients with NED at baseline (i.e. no TLs and no NTLs), evaluation of overall visit response at each visit will be based on absence/presence of new lesions. If no TLs and no NTLs are recorded at a visit, both the TL and NTL visit response will be recorded as NA and the overall visit response will be NED if there is no new lesion.

If a patient has had a tumour assessment which cannot be evaluated then the patient will be assigned a visit response of not evaluable (NE) (unless there is evidence of progression in which case the response will be assigned as PD).

Table 2 TL Visit Responses

Visit Responses	Description
Complete Response (CR)	Disappearance of all TLs since baseline. Any pathological lymph nodes selected as TLs must have a reduction in short axis to <10 mm
Partial Response (PR)	At least a 30% decrease in the sum of diameters of TL, taking as reference the baseline sum of diameters as long as criteria for PD are not met.
Progressive Disease (PD)	At least a 20% increase in the sum of diameters of TLs taking as reference the smallest sum on study (this includes the baseline sum if that is the smallest on study). In addition to the relative increase of 20%, the sum must also indicate an absolute increase of at least 5 mm
Stable Disease (SD)	Neither sufficient shrinkage to qualify for PR nor sufficient increase to qualify for PD
Not Evaluable (NE)	Only relevant if any of the TLs were not assessed or not evaluable or had a lesion intervention at this visit. Note: If the sum of diameters meets the progressive disease criteria, progressive disease overrides not evaluable as a TL response
Not Applicable (NA)	No TLs are recorded at baseline

Rounding of TL data

For calculation of PD and PR for TLs, percentage changes from baseline and previous minimum should be rounded to 1 decimal place before assigning a TL response. For example 19.95% should be rounded to 20.0% but 19.94% should be rounded to 19.9%

Missing TL data

For a visit to be evaluable, all TL measurements should be recorded. However, a visit response of PD should still be assigned if any of the following occurred:

- A new lesion is recorded.
- A NTL visit response of PD is recorded.
- The sum of TLs is sufficiently increased to result in a 20% increase, and an absolute increase of ≥ 5 mm, from nadir even assuming the non-recorded TLs have disappeared.

Note: the nadir can only be taken from assessments where all the TLs had a lesion diameter recorded.

Lymph nodes

For lymph nodes, if the size reduces to < 10 mm then these are considered non-pathological. However a size will still be given and this size should still be used to determine the TL visit response as normal. In the special case where all lymph nodes are < 10 mm and all other TLs are 0 mm then although the sum may be > 0 mm the calculation of TL response should be over-written as a CR.

TL visit responses subsequent to CR

A CR can only be followed by CR, PD or NE. If a CR has occurred then the following rules at the subsequent visits must be applied:

- Step 1: If all lesions meet the CR criteria (i.e. 0 mm or < 10 mm for lymph nodes) then response will be set to CR irrespective of whether the criteria for PD of TL is also met i.e. if a lymph node longest diameter (LD) increases by 20% but remains < 10 mm.
- Step 2: If some lesion measurements are missing but all other lesions meet the CR criteria (i.e. 0 mm or < 10 mm for lymph nodes) then response will be set to NE irrespective of whether when referencing the sum of TL diameters the criteria for PD is also met.
- Step 3: If not all lesions meet the CR criteria and the sum of lesions meets the criteria for PD then response will be set to PD
- Step 4: If after steps 1 – 3 a response can still not be determined the response will be set to remain as CR

TL too big to measure

If a TL becomes too big to measure this should be indicated in the database and a size ('x') above which it cannot be accurately measured should be recorded. If using a value of x in the calculation of TL response would not give an overall visit response of PD, then this will be flagged and reviewed by the study team blinded to treatment assignment. It is expected that a visit response of PD will remain in the vast majority of cases.

TL too small to measure

If a TL becomes too small to measure a value of 5 mm will be entered into the database and used in TL calculations, unless the radiologist has indicated and entered a smaller value that can be reliably measured. If a TL response of PD results then this will be reviewed by the study team blinded to treatment assignment.

Irradiated lesions/lesion intervention during the study

According to the study design, it is possible that patients have some residual disease that has been irradiated prior to their study entry. For this reason, previously irradiated lesions may be selected as TLs.

Any TL (including lymph nodes), which has had intervention during the study (for example, irradiation / palliative surgery / embolisation), should be handled in the following way and once a lesion has had intervention then it should be treated as having intervention for the remainder of the study noting that an intervention will most likely shrink the size of tumours:

- Step 1: the diameters of the TLs (including the lesions that have had intervention) will be summed and the calculation will be performed in the usual manner. If the visit response is PD this will remain as a valid response category.
- Step 2: If there was no evidence of progression after step 1, treat the lesion diameter (for those lesions with intervention) as missing and scale up as described below, as long as there remain $\leq 1/3$ of the TLs with interventions. If the scaling results in a visit response of PD then the patient would be assigned a TL response of PD.
- Step 3: If after both steps PD has not been assigned, then if appropriate, a scaled sum of diameters will be calculated (as long as $\leq 1/3$ of the TLs with interventions), and PR or SD then assigned as the visit response. Patients with intervention are evaluable for CR as long as all non-intervened lesions are 0 (or <10 mm for lymph nodes) and the lesions that have been subjected to intervention also has a value of 0 recorded.

At subsequent visits the above steps will be repeated to determine the TL and overall visit response. When calculating the previous minimum, lesions with intervention should be treated as missing and scaled up where appropriate (as per step 2 above).

Scaling (applicable only for irradiated lesions/lesion intervention during the study)

If > 1/3 of TL measurements are treated as missing (because of intervention) then TL response will be NE, unless the sum of diameters of non-missing TL would result in PD (i.e. if using a value of 0 for missing lesions, the sum of diameters has still increased by > 20% or more compared to nadir and the sum of TLs has increased by 5mm from nadir).

If ≤ 1/3 of the TL measurements are treated as missing (because of intervention) then the results will be scaled up (based on the sizes at the nadir visit to give an estimated sum of diameters and this will be used in calculations; this is equivalent to comparing the visit sum of diameters of the non- missing lesions to the nadir sum of diameters excluding the lesions with missing measurements).

Example of scaling

Lesion	Longest diameter at nadir visit	Longest diameter at follow-up visit
1	7.2	7.1
2	6.7	6.4
3	4.3	4.0
4	8.6	8.5
5	2.5	Intervention
Sum	29.3	26

Lesion 5 has had an intervention at the follow-up visit.

The sum of lesions 1-4 at the follow-up is 26 mm. The sum of the corresponding lesions at baseline visit is 26.8 mm.

Scale up as follows to give an estimated TL sum of 28.4mm:

$$\frac{26}{26.8} \times 29.3 = 28.4\text{mm}$$

Lesions that split in two

If a TL splits in two, then the LDs of the split lesions should be summed and reported as the LD for the lesion that split.

Lesions that merge

If two TLs merge, then the LD of the merged lesion should be recorded for one of the TL sizes and the other TL size should be recorded as 0 mm.

Change in method of assessment of TLs

CT and MRI are the only methods of assessment that can be used within the trial. If a change in method of assessment occurs between CT and MRI, this will be considered acceptable and no adjustment within the programming is needed.

If a change in method involves clinical examination (e.g. CT changes to clinical examination or vice versa), any affected lesions should be treated as missing.

3.1.5 Site investigator assessment using RECIST 1.1: NTLs and new lesions

At each visit an overall assessment of the NTL response should be recorded by the investigator. This section provides the definitions of the criteria used to determine and record overall response for NTL at the investigational site at each visit.

NTL response will be derived based on the investigator's overall assessment of NTLs as follows:

Table 3 NTL Visit Responses

Visit Responses	Description
Complete Response (CR)	Disappearance of all NTLs present at baseline with all lymph nodes non-pathological in size (<10 mm short axis).
Progression (PD)	Unequivocal progression of existing NTLs. Unequivocal progression may be due to an important progression in one lesion only or in several lesions. In all cases the progression MUST be clinically significant for the physician to consider changing (or stopping) therapy.
Non-CR/Non-PD	Persistence of one or more NTLs with no evidence of progression.
Not Evaluable (NE)	Only relevant when one or some of the NTLs were not assessed and, in the investigator's opinion, they are not able to provide an evaluable overall NTL assessment at this visit. Note: For patients without TLs at baseline, this is relevant if any of the NTLs were not assessed at this visit and the progression criteria have not been met.
Not Applicable (NA)	Only relevant if there are no NTLs at baseline

To achieve 'unequivocal progression' on the basis of NTLs, there must be an overall level of substantial worsening in non-target disease such that, even in the presence of SD or PR in TLs, the overall tumour burden has increased sufficiently to merit a discontinuation of

therapy. A modest ‘increase’ in the size of one or more NTLs is usually not sufficient to qualify for unequivocal progression status.

Details of any new lesions will also be recorded with the date of assessment. The presence of one or more new lesions is assessed as progression.

A lesion identified at a follow up assessment in an anatomical location that was not scanned at baseline is considered a new lesion and will indicate disease progression.

The finding of a new lesion should be unequivocal: i.e. not attributable to differences in scanning technique, change in imaging modality or findings thought to represent something other than tumour.

New lesions will be identified via a Yes/No tick box. The absence and presence of new lesions at each visit should be listed alongside the TL and NTL visit responses.

A new lesion indicates progression so the overall visit response will be PD irrespective of the TL and NTL response.

If the question ‘Any new lesions since baseline’ has not been answered with Yes or No and the new lesion details are blank this is not evidence that no new lesions are present and should be treated as NE in the derivation of overall visit response.

Symptomatic deterioration is not a descriptor for progression of NTLs: it is a reason for stopping study therapy and will not be included in any assessment of NTLs.

Patients with ‘symptomatic deterioration’ requiring discontinuation of treatment without objective evidence of disease progression at that time should continue to undergo tumour assessments where possible until objective disease progression is observed.

3.1.6 Site investigator assessment using RECIST 1.1: overall visit response

Table 4 defines how the previously defined TL and NTL visit responses will be combined with new lesion information to give an overall visit response.

Table 4 Overall Visit Responses

Target Lesions	Non-target lesions	New Lesions	Overall Response
CR	CR	No	CR
CR	NA	No	CR
NA	CR	No	CR
CR	Non CR/Non PD	No	PR
CR	NE	No	PR
PR	Non PD or NE	No	PR

Table 4 Overall Visit Responses

Target Lesions	Non-target lesions	New Lesions	Overall Response
SD	Non PD or NE	No	SD
NA	Non CR/Non PD	No	SD (Non CR/Non PD)
NE	Non PD or NE	No	NE
NA	NE	No	NE
PD	Any	Yes or No	PD
Any	PD	Yes or No	PD
Any	Any	Yes	PD
NA	NA	No	NED

CR = complete response, PR = partial response, SD = stable disease, PD = progressive disease, NE = not evaluable, NED = no evidence of disease, NA = not applicable (only relevant if there were no TL/NL at baseline).

3.2 Outcome Variables

All RECIST assessments, whether scheduled or unscheduled, will be included in the calculations. This is also regardless of whether a patient discontinues investigational product.

RECIST 1.1 outcomes (ie PFS, ORR etc.) will be derived using the overall visit responses and relevant dates from the BICR. This will be repeated using the programmatically derived overall visit responses from investigator RECIST 1.1 assessments.

3.2.1 Co-primary efficacy outcome endpoints

The co-primary endpoints are OS and PFS.

3.2.1.1 Overall survival (OS)

OS is defined as the time from the date of randomisation until death due to any cause (i.e., date of death or censoring – date of randomisation + 1). Any patient not known to have died at the time of analysis will be censored based on the last recorded date on which the patient was known to be alive (SUR_DAT, recorded within the SURVIVE module of the eCRF).

Note: Survival calls will be made in the week following the date of DCO for the analysis, and if patients are confirmed to be alive or if the death date is post the DCO date these patients will be censored at the date of DCO. The status of ongoing, withdrawn (from the study) and “lost to follow-up” patients at the time of the final OS analysis should be obtained by the site personnel by checking the patient’s notes, hospital records, contacting the patient’s general practitioner and checking publicly-available death registries. In the event that the patient has actively withdrawn consent to the processing of their personal data, the vital status of the patient can be obtained by site personnel from publicly-available resources where it is possible to do so under applicable local laws.

Note that for any OS analysis performed prior to the final OS analysis, in the absence of survival calls being made, it may be necessary to use all relevant CRF fields to determine the last recorded date on which the patient was known to be alive for those patients still on treatment (since the SURVIVE module is only completed for patients off treatment if a survival sweep is not performed). The last date for each individual subject is defined as the latest among the following dates recorded on the CRFs:

- AE start and stop dates
- Admission and discharge dates of hospitalization
- Study treatment date
- End of treatment date
- Laboratory test dates
- Date of vital signs
- Disease assessment dates on RECIST CRF
- Start and stop dates of alternative anticancer treatment
- Date last known alive on survival status CRF
- End of study date

3.2.1.2 Progression free survival (PFS)

PFS (per RECIST 1.1 as assessed by BICR) will be defined as the time from the date of randomisation until the date of the first objective disease progression or death (by any cause in the absence of progression) regardless of whether the patient withdraws from randomised therapy or receives another anti-cancer therapy prior to progression (i.e., date of PFS event or censoring – date of randomisation + 1). Patients who have not progressed or died at the time of analysis will be censored at the time of the latest date of assessment from their last RECIST 1.1 assessment. However, if the patient progresses or dies after 2 or more missed visits, the patient will be censored at the time of the latest RECIST 1.1 assessment prior to the two missed visits.

Given the scheduled visit assessment scheme (ie eight-weekly for the first 48 weeks then twelve-weekly thereafter) the definition of 2 missed visits will change. If the previous RECIST assessment is less than study day 274 (ie week 39) then two missing visits will equate to 18 weeks since the previous RECIST assessment, allowing for early and late visits (ie, 2 x 8 weeks + 1 week for an early assessment + 1 week for a late assessment = 18 weeks). If the two missed visits occur over the period when the scheduled frequency of RECIST assessments changes from eight-weekly to twelve-weekly this will equate to 22 weeks (ie,

take the average of 8 and 12 weeks which gives 10 weeks and then apply same rationale hence 2×10 weeks + 1 week for an early assessment + 1 week for a late assessment = 22 weeks). The time period for the previous RECIST assessment will be from study days 274 to 344 (ie week 39 to week 49). From week 49 onwards (when the scheduling changes to twelve-weekly assessments), two missing visits will equate to 26 weeks (ie 2×12 weeks + 1 week for an early assessment + 1 week for a late assessment = 26 weeks). If the patient has no visits or does not have baseline data they will be censored at study day 1 unless they die within 2 visits of baseline (16 weeks plus 1 week allowing for a late assessment within the visit window).

The PFS time will always be derived based on scan/assessment dates not visit dates.

PFS will also be obtained using the algorithm described above for the RECIST site investigator tumour data.

RECIST 1.1 assessments/scans contributing towards a particular visit may be performed on different dates. The following rules will be applied:

- The date of progression will be determined based on the earliest of the scan dates of the component that triggered the progression for the adjudicated reviewer selecting PD or of first reviewer where both select PD as a time point response and there is no adjudication for central review (BICR) data.
- For investigational assessments, the date of progression will be determined based on the earliest of the RECIST assessment/scan dates of the component that indicates progression
- When censoring a patient for PFS the patient will be censored at the latest of the dates contributing to a particular overall visit assessment.

Note: For TLs, only the latest scan date is recorded out of all scans performed at that assessment for the TLs and similarly for NTLs only the latest scan date is recorded out of all scans performed at that assessment for the NTLs. Additionally, PFS will be obtained using the algorithm described above for the RECIST BICR data, but following a modification whereby any objective disease progression must be confirmed by the next scheduled scan. The confirmatory scan must be no sooner than 4 weeks after the initial suspected progression. If disease progression is confirmed (or disease progression occurs and no further scans are recorded) then the date of progression will be when it was originally observed. Patients with a single disease progression and no further tumour assessment scans will be treated as PD in the analysis.

In the absence of clinically significant deterioration the investigational site is advised to continue the patient on study drug until progression has been confirmed.

For exploratory purposes, PFS will also be obtained using the irRECIST 1.1 data provided by BICR. Objective disease progressions also require confirmation under this approach.

Time to first subsequent therapy or death (TFST)

As a supportive summary to PFS, time to start of first subsequent therapy or death (TFST) will be derived. TFST is defined as the time from randomisation to the start date of the first subsequent therapy after discontinuation of treatment, or death, whichever is earlier (i.e. date of first subsequent anti-cancer therapy/death or censoring – date of randomisation + 1). Any patient not known to have had a first subsequent therapy will be censored at the last date that the patient was known not to have received a first subsequent therapy (obtained from the TTSCAPRX form). If a patient terminated the study for reason other than death before first subsequent therapy, these patients will be censored at the earliest of their known to be alive and termination dates. Patients not receiving randomised treatment would have TFST calculated in the same way, i.e. time from date of randomisation to the subsequent therapy or death. Note that the censoring for those patients without a subsequent therapy will align with their OS.

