3. PRIMARY, SECONDARY AND EXPLORATORY VARIABLES

3.1 Derivation of RECIST Visit Responses

For all patients, the RECIST version 1.1 (see further Appendix F of the CSP and Independent Review Charter) tumour response data will be used to determine each patient's visit response. It will also be used to determine if and when a patient has progressed and also their best objective response.

The baseline tumour assessment is part of the screening procedures and should be performed within 0 to 42 days after the end of chemoradiation therapy and no more than 28 days before the start of study drug. For patients who are recovering from toxicities associated with prior treatment, randomisation may be delayed by up to 42 days from the end of the chemoradiation therapy.

Efficacy for all patients will be assessed by objective tumour assessments every 8 weeks (relative to the date of randomisation) for the first 12 months, then every 12 weeks thereafter, until confirmed objective disease progression as defined by RECIST 1.1 (irrespective of the reason for stopping study drug and/or subsequent therapy). For patients who discontinue study drug due to toxicity or a reason other than confirmed PD, objective tumour assessments should be continued every 8 weeks for 48 weeks (relative to the date of randomisation) then every 12 weeks thereafter until confirmed objective disease progression. If an unscheduled assessment is performed, and the patient has not progressed, every attempt should be made to perform the subsequent assessments at their scheduled visits.

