Additionally, summary statistics for the number of weeks between the time of progression and the last RECIST assessment prior to progression will be presented for each treatment group.

Summaries of the number and percentage of patients who miss two or more consecutive RECIST assessments will be presented for each treatment group.

All of the collected RECIST 1.1 data will be listed for all randomised patients. In addition, a summary of new lesions (i.e., sites of new lesions) will be produced.

Sensitivity Analyses

The following sensitivity analyses will be performed:

- Evaluation-Time bias

Sensitivity analyses will be performed to assess possible evaluation-time bias that may be introduced if scans are not performed at the protocol-scheduled timepoints. The midpoint between the time of progression and the previous RECIST assessment will be analysed using a stratified log-rank test, as described for the co-primary analysis of PFS. For patients whose death was treated as PFS event, the date of death will be used to derive the PFS time used in the analysis. This approach has been shown to be robust to even highly asymmetric assessment schedules ([Sun and Chen 2010](#)). To support this analysis, the mean of subject-level average inter-assessment times will be tabulated for each treatment. This approach will use the BICR data.

- Attrition bias

Attrition bias will be assessed by repeating the co-primary PFS analysis except that the actual PFS event times, rather than the censored times, of patients who progressed or died in the absence of progression immediately following two, or more, tumour assessments will be included. In addition, patients who take subsequent therapy prior to their last evaluable RECIST assessment or progression or death will be censored at their last assessment prior to taking the subsequent therapy. This analysis will be supported by a Kaplan-Meier plot of the time to censoring where the censoring indicator of the PFS analysis is reversed. This approach will use the BICR data.

- Ascertainment bias

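### The 18-week definition of two missed visits does not fit the baseline scan: a progression found on time at week 16 after one missed scan can be censored at baseline

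*SAP*

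**What the plan says.** SAP 3.2.1.2 states the rule first in words. If progression or death comes after two or more missed visits, "the patient will be censored at the time of the latest RECIST 1.1 assessment prior to the two missed visits". It then gives the rule a length for the 8-weekly part of the schedule: "If the previous RECIST assessment is less than study day 274 (ie week 39) then two missing visits will equate to 18 weeks". The clock starts at the previous assessment: "two missing visits will equate to 18 weeks since the previous RECIST assessment, allowing for early and late visits". The derivation is "2 x 8 weeks + 1 week for an early assessment + 1 week for a late assessment = 18 weeks". No exception is written for a previous assessment that is the baseline scan.

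SAP 3.1 allows the baseline scan to be "no more than 28 days before the start of study drug" and times the follow-up scans from randomisation. Notes to Protocol Table 1 require study drug within 24 hours of randomisation. SAP 2.2 refers to baseline as a RECIST 1.1 assessment.

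PFS time is "date of PFS event or censoring – date of randomisation + 1". The fallback to study day 1 covers only patients with no visits or no baseline data, "unless they die within 2 visits of baseline (16 weeks plus 1 week allowing for a late assessment within the visit window").

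**The concern.** The 18 weeks assume that the previous scan was at most one week early. That is true of a scheduled on-study scan, but the baseline scan can be about four weeks early. If only the week-8 scan is missed, the baseline scan is the previous assessment, and the gap to an on-schedule week-16 scan can exceed the limit. The numerical definition then counts two missed visits where the wording of the rule counts one.

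At stake is the derivation of a co-primary endpoint. A centrally read progression is replaced by censoring at a date before randomisation, and the SAP does not say how a negative time is handled. Two programmers, one following the words and one the number, could reach different event counts. SAP section 6 explains that the censoring date was last revised so that all available tumour follow-up is used; losing an on-schedule progression runs against that aim. The same rule feeds TTDM (SAP 3.2.2.7), and best objective response (SAP 3.2.2.2) ignores progressions censored in this way.

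**Working it through.** **Inputs.** Limit of 18 weeks from the previous assessment (SAP 3.2.1.2). Baseline scan up to 28 days before study drug (SAP 3.1; Protocol Table 1 footnote f; Protocol Appendix F 4.1). Drug within 24 hours of randomisation (Protocol Table 1). Scans every 8 weeks from randomisation (SAP 3.1), window ±7 days (SAP 3.2.2.2). Let b be the number of days from the baseline scan to randomisation.

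**The plan's figure reproduces.** 2×8 + 1 + 1 = 18 weeks = 126 days.

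**It works between on-study scans.** With one missed scan, the longest in-window gap is week 8 a week early to week 24 a week late: (168 + 7) − (56 − 7) = 126 days. With two missed scans, the shortest is week 8 a week late to week 32 a week early: (224 − 7) − (56 + 7) = 154 days. A limit of more than 126 days separates the two.

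**It fails from baseline.** With week 8 missed and progression at week 16, the gap is 112 + w + b days, where w is −7, 0 or +7. It exceeds 126 when b > 14 − w:

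| Week-16 scan | Gap exceeds 18 weeks when | Gap at b = 28 |
|---|---|---|
| A week early | b ≥ 22 | 133 days (19 weeks) |
| On time | b ≥ 15 | 140 days (20 weeks) |
| A week late | b ≥ 8 | 147 days (21 weeks) |

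At b = 14 with an on-time scan the gap is exactly 126 days, and the outcome depends on whether the limit is > or ≥, which the SAP does not say.

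**Resulting PFS time.** Censoring at the baseline scan gives −b + 1: −14 at b = 15 and −27 at b = 28. The day 1 fallback does not apply, because the patient has baseline data and a week-16 visit.

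**Illustrative size (assumptions, not document figures).** The documents give neither the spread of b nor the rate of missed week-8 scans.
- Share of on-time week-16 progressions affected: 14/29 = 48% if b is even over 0 to 28 days. But b cannot exceed the time from the end of chemoradiation to randomisation. If that time is even over 1 to 42 days and b is even over its permitted range, the share is 26% (11% for a scan a week early, 50% for a week late).
- PFS events by week 16 (112 days = 3.68 months), for 234 and 468 patients with exponential medians of 10 and 15 months: 234×(1 − 2^(−3.68/10)) + 468×(1 − 2^(−3.68/15)) ≈ 53 + 73 = 126. This includes deaths, so it is too high for the present purpose.
- If 2% to 5% of patients miss week 8: 126×0.02×0.26 ≈ 0.7 to 126×0.05×0.48 ≈ 3 events, at most 3/458 = 0.7%.

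**Check of the remedy.** Counted from randomisation, progression at week 16 after one missed scan is 105 to 119 days, within 126. Progression at week 24 after two missed scans is at least 168 − 7 = 161 days, still censored. The existing 18 weeks therefore suffice.

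**The case against.** The strongest reply is that the words govern. The rule speaks of two or more missed visits, the 18 weeks only put it into practice for an 8-weekly schedule, and the SAP never says that the clock starts at baseline. For deaths without follow-up scans it uses 16 + 1 weeks, with no allowance for an early visit, and the matching response rule in SAP 3.2.2.2 classes deaths within 17 weeks of randomisation as progression. A programmer who follows the words keeps the event. This is fair as to intent, but it does not remove the conflict: the definition is numerical, baseline is the only earlier assessment such a patient has, and no exception is written.

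The point on size stands. Anyone randomised within 14 days of finishing chemoradiation cannot be affected by an on-time week-16 scan. Protocol 4.1 encourages sites to complete screening within the first 14 days, and Appendix F asks for the scan as close as possible to study drug. Any unscheduled scan before week 16 resets the clock. Against this, SAP 2.2 flags only baseline scans more than 42 days before randomisation, so some values of b may exceed 28.

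The attrition-bias analysis (SAP 4.2.1.2) is meant to restore actual event times, and patients who miss two or more consecutive assessments are tabulated by arm. That mitigation is partial, because the same analysis also censors at subsequent therapy and so does not isolate this effect.

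A reader might infer that the midpoint analysis is at fault in the same way, since "The midpoint between the time of progression and the previous RECIST assessment will be analysed using a stratified log-rank test". For progression at week 8 and a baseline scan 28 days before randomisation, the midpoint is (−28 + 56)/2 = 14 days after randomisation, against 28 if anchored at randomisation. It is not before randomisation, progression does lie between the two scans, and this is a sensitivity analysis. Nor do the documents support extending the point to the PRO rules: Protocol Table 1 schedules questionnaires at the randomisation visit as well as at screening, so a baseline four weeks old is not the normal case.

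**Conclusion.** Wrong as written, minor impact. The arithmetic is certain given the literal text: one missed scan is classed as two when the baseline scan is 15 or more days before randomisation and the week-16 scan is on time (8 or more if a week late, 22 or more if a week early). The progression is then lost and the PFS time is negative.

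How many patients this touches cannot be computed from the documents. Under the assumptions shown it is roughly one to three events, and probably a few at most, out of 458.

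A reader might infer that about half of such progressions are lost, or that the treatment comparison is biased. The documents support neither. The 48% needs an even spread of scan dates that ignores the limit set by the time since chemoradiation. The baseline scan precedes allocation and the trial is double-blind, so b should be balanced between arms, and no differential loss is shown. The PFS conclusion is unlikely to change.

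**What to change.** Add one clause to SAP 3.2.1.2: when the previous assessment is the baseline scan, it is treated as study day 1 for this rule, so that the 18 weeks run from randomisation and any resulting censoring is at study day 1. Put the same clause in SAP 3.2.2.7 for TTDM; best objective response follows automatically. The 18-week length need not change, and the 17-week provision for deaths without any visit can stay.

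State whether the limit is > or ≥. Strictly greater is the version that fits the wording, because a gap of exactly 126 days can arise with a single missed on-study scan.

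Anchoring the midpoint analysis at the later of randomisation and the previous assessment is optional.

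The cost is one clause in two places and trivial programming. The protocol synopsis records that the planned analyses were concluded by Amendment 07. For those analyses, the useful step is to state how the rule was programmed and to count the patients with week-16 progression and no scan between baseline and week 16.
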